**Protocol:**

Following the consent process the participants will be asked to participate in the following:

1. Participants will complete Central Sensitization Inventory (CSI) and the Columbia Suicide Severity Rating (CSSR) as well as any necessary labs. These will be done in person at the time of consent/enrollment. If the participant answers Yes on any of the CSSR questions, they will exit the study. If any participant scores < 40 on the CSI, they will exit the study.
2. If they still qualify for the study, they will complete (1) the Baseline Subject Demographic form, (2) the Pain, Enjoyment of Life and General Activity form (PEG-3), and (3) the Knee Injury and Osteoarthritis Outcomes Score (KOOS). These will be done in person at the pre-op visit.

3. All participants will meet with a physical therapist prior to surgery to assess baseline functional levels using established assessment surveys. The approximate time to complete these assessments is 30 minutes.

The surveys used include: Timed Up and Go (TUG)

Stand-Up, Sit-Down (STS)

Patient-Specific Functional Scale Assessment (PSFS)

3. Participants are randomized at the pre-op visit to standard of care vs study treatment arm using a computer-generated block randomization sequence. The allocation of concealment will be ensured using a sealed envelope technique.

4. If the participant is not randomized to the study medication arm, they will proceed with usual peri-operative management.

5. If the participant is randomized to study medication arm, they will be directed to the UIHC Discharge Pharmacy to retrieve the study drug. Additionally, they will be provided information about the medication, possible side effects and dosing schedule.

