8. All participants will be contacted by the study pharmacist about 7 days after surgery by telephone. The pharmacist will also determine the amount of other pain medications that have been needed for pain relief for all participants. The goal of this assessment is to determine how the participant is faring with the study medication (if randomized to the study medication arm) and other pain medications. The pharmacist will review the study medication dosing schedule with these participants and re-assess with the CSSR scale. If the participant did not tolerate the study medication they will exit the study and continue to receive standard post-surgical care. If the patient answers Yes to any of the CSSR items, they will be advised to seek out behavioral healthcare. If they answer Yes to questions 4,5, or 6, they will be advised to seek immediate medical attention or local EMS will be contacted by the pharmacist. They will stop the study medication and exit the study at that time.

9. Patients will have a 6-week post-operative visit with their surgical team and research study team. At this time, all participants will again complete the Knee Injury and Osteoarthritis Outcomes Score (KOOS), the PEG-3 pain survey, and the Central Sensitization Inventory (CSI) assessments. Also the participant will be asked to report how much opioid medication (if any) they are taking and the physical therapist will repeat the functional tests (TUG, STS, PSFS). The time to complete these evaluations is approximately 60 minutes.

10. This will complete the study participation.

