#### Analysis/Statistical Plan:

Treatment-stratified summary statistics will be calculated for all baseline measures, including demographics and clinical outcomes. Categorical measures will be presented as counts and percentages. Continuous measures will be assessed for normality and presented as either means and standard deviations or medians and interquartile ranges. Assessments of between-group differences will be conducted for all baseline non-subscale measures using Fisher's exact, two-sample t-, or Wilcoxon rank sum tests. Between-group differences for baseline subscale measures (following a 5-point Likert scale) will be assessed using cumulative logistic regression to utilize the ordinality of the measure.

Between-group changes (baseline to week 6) in the primary outcome (KOOS- ADL) and secondary outcomes (KOOS subscale scores (pain, symptoms, sports/recreation, and quality of life subscales, pain scores, differences Timed Up and Go Test (TUG), the Sit-to-Stand Test (STS) and the Patient Specific Functional Scale (PSFS) will be assessed by calculating the within-subject differences. Distributions for each outcome's 6-week change will be examined. Measures with normally distributed differences will follow the two-sample t-test to compare changes between treatment groups, and measures with non-normally distributed differences will follow the Wilcoxon rank sum test. Tests with p-values < 0.05 will be considered statistically significant.

As an exploratory outcome, we will investigate the relationship between 6-week changes in CSI scores and changes in pain and function outcomes. Associations between normally and non-normally distributed measures will be investigated using Pearson's and Spearman's correlations, respectively.

Adverse effects will be calculated for each treatment group and presented counts and percentages.

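### Does the plan need a rule for reading a significant secondary outcome when KOOS-ADL is not significant?

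*Combined protocol and SAP*

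**What the plan says.** The Analysis/Statistical Plan section of the combined document has three tiers. The first two appear in one sentence, which begins "Between-group changes (baseline to week 6) in the primary outcome (KOOS- ADL) and secondary outcomes". The secondaries follow: "KOOS subscale scores (pain, symptoms, sports/recreation, and quality of life subscales, pain scores, differences Timed Up and Go Test (TUG", and then "the Sit-to-Stand Test (STS) and the Patient Specific Functional Scale (PSFS) will be assessed". Each outcome gets one between-group comparison of its 6-week change, by two-sample t-test or Wilcoxon rank sum test depending on its distribution. The third tier is the analysis of CSI change, introduced by "As an exploratory outcome, we will investigate the relationship between 6-week changes in CSI scores".

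The decision rule is a single sentence: "Tests with p-values < 0.05 will be considered statistically significant". It does not separate the primary from the secondaries and does not state sidedness. Nothing in the document mentions multiplicity adjustment, a testing order or gatekeeping. Nothing says whether secondary results are confirmatory or supportive.

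The entry for pain scores is not defined further. Apart from KOOS, the only named pain survey collected at both time points is the PEG-3. At the pre-op visit (Protocol, step 2) it is "the Pain, Enjoyment of Life and General Activity form (PEG-3"; at the 6-week visit (step 9) it is "the PEG-3 pain survey". I therefore count it as one outcome.

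**The concern.** One threshold covers nine tests, and eight of them are secondary. A 5% error rate describes a secondary picked out before the data are seen. It does not describe one picked from eight because it fell below 0.05. If KOOS-ADL shows nothing and, say, TUG or the KOOS pain subscale has p < 0.05, a report calling that result statistically significant would follow the plan to the letter. Four of the secondaries come from the same questionnaire as the primary and the others measure pain or function, so any of them could be presented as the benefit of pregabalin. What is at stake is the strength of a claim made after a null primary, not the primary result itself.

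**Working it through.** The documents state no sample size, power or family-wise error rate, so there is no plan figure to reproduce.

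**Inputs from the Analysis/Statistical Plan**
- Threshold per test: 0.05.
- Primary outcomes: 1 (KOOS-ADL).
- Secondary outcomes: 4 KOOS subscales + 1 pain score + TUG + STS + PSFS = 8.

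**Assumptions, not in the documents**
- No true effect on any outcome.
- Two-sided tests with approximately normal test statistics.
- A common correlation ρ between test statistics, varied from 0 to 0.9.

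**Independent case (ρ = 0)**
- At least one significant secondary: 1 − 0.95^8 = 0.337.
- That together with a non-significant KOOS-ADL: 0.95 × 0.337 = 0.320.
- The same, with the secondary favouring pregabalin: 0.95 × (1 − 0.975^8) = 0.95 × 0.183 = 0.174.

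**Correlated case (ρ > 0)**

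Let c = 1.96, let u be the shared normal factor, and define
- A(u) = Φ((c − √ρ·u)/√(1−ρ)) − Φ((−c − √ρ·u)/√(1−ρ)), the chance that one test is non-significant given u;
- B(u) = Φ((c − √ρ·u)/√(1−ρ)), the chance that one test does not significantly favour pregabalin given u.

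Then
- either direction: 0.95 − ∫ φ(u)·A(u)^9 du;
- favouring pregabalin: 0.95 − ∫ φ(u)·A(u)·B(u)^8 du.

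For example, at ρ = 0.5 the first integral is 0.731, so the either-direction figure is 0.95 − 0.731 = 0.219.

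Chance of a non-significant KOOS-ADL with at least one significant secondary:

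| ρ | Either direction | Favouring pregabalin |
|---|---|---|
| 0 | 32.0% | 17.4% |
| 0.3 | 27.6% | 14.0% |
| 0.5 | 21.9% | 11.0% |
| 0.7 | 15.2% | 7.6% |
| 0.8 | 11.6% | 5.8% |
| 0.9 | 7.4% | 3.7% |

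Simulation with 2,000,000 draws gives 32.0%, 21.9% and 7.4% in either direction at ρ = 0, 0.5 and 0.9.

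**Sensitivity**
- Mixed correlations (the five KOOS scales and the pain score at 0.7 with one another, all other pairs 0.3): 22% in either direction, 11% favouring pregabalin.
- Count of secondaries, either direction, ρ = 0.9 to 0: seven give 6.9% to 28.7%, nine give 7.8% to 35.1%.
- One-sided 0.05 tests, ρ = 0.9 to 0: 6% to 32%.

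The zero-correlation row is an outer bound. Four of the eight secondaries are subscales of one questionnaire, so independence is not credible.

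**What added wording would change**

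A two-sided t-test has p < 0.05 exactly when its 95% confidence interval excludes zero. If secondaries were reported as unadjusted estimates with intervals and called supportive, the t-tested secondaries would show the pattern as often as before. Only an adjustment lowers the frequency. Bonferroni at 0.05/8 = 0.00625 would bring the either-direction figure to about 4.7%, 2.9% and 0.2% at ρ = 0, 0.5 and 0.9, but each secondary would then face a much stricter threshold.

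**The case for a change.** The strongest case for a change is that the ranking of outcomes is only a set of labels, and the one decision rule in the plan ignores them. A sentence stating that secondary p-values are unadjusted and supportive would cost almost nothing. It would leave data collection, the primary estimate and primary power alone, and it would forestall a claim built on a selected secondary. At correlations of 0.7 or less, the favourable-direction chance of 7.6% or more is well above the 2.5% a reader would attach to one secondary named in advance.

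The textual point and the arithmetic both stand. They do not show that following the plan gives a wrong analysis. The plan nowhere says that a significant secondary establishes efficacy or makes up for a null primary. All the secondaries are listed beforehand, so a reader can see how many tests stand behind any one result. The remaining risk is selective emphasis in a later report, and the ordinary reading of a secondary outcome already guards against that. The remedy is also not unique: unadjusted and supportive, gatekeeping behind KOOS-ADL, or a Holm procedure would each be defensible. Choosing among them is a preference, not the correction of an error.

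**Conclusion.** No change to the plan follows. The unwritten point is one of interpretation, and analysts fill it sensibly: KOOS-ADL carries the conclusion, secondaries support it, and the CSI correlations are exploratory. KOOS-ADL is tested once at 0.05, so its nominal error rate is unaffected by the number of secondaries, and each secondary taken singly also keeps 5%.

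The pattern at issue, a null KOOS-ADL beside at least one secondary significantly favouring pregabalin, has a chance of about 4% to 14% at common correlations of 0.9 to 0.3, or 7% to 28% in either direction. This rests on no true effect, two-sided tests, normal test statistics, and pain scores counted as one outcome. None of the correlations comes from the documents. The figures are a reason to read a lone significant secondary with caution. They describe chance findings that a supportive-only label would leave equally frequent, so they do not measure an error that rewording would remove.

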**Dosing Schedule**

Pre-surgery (days 1-7) pregabalin 75mg twice daily

Post-surgery (days 1-7) pregabalin 150mg twice daily, then (days 8-14) pregabalin 75mg twice daily

6. Day of Surgery (DOS): Someone from the research team will meet with all participants in DOSA to (1) answer any questions about continued participation in the study. For those participants in the study medication arm, the research team member will also evaluate if they have (2) completed the study medication schedule, (3) determine if they have noticed any side effects from the medication (including the CSSR scale), and (4) remind the participant of post-surgical medication dosing schedule. If the participant did not tolerate the study medication they will exit the study and continue to receive standard surgical care. If the patient answers Yes to any of the CSSR items, they will be advised to seek out behavioral healthcare. If they answer Yes to questions 4,5, or 6, they will be immediately taken to the ED by study team member for evaluation. They will stop the study medication and exit the study at that time. Proceeding with surgery will be deferred to the primary surgery team. This visit is expected to take less than 15 minutes.

7. All participants undergo a post-operative Physical Therapy assessment, which normally

occurs within a week of surgery per standard of care. At that time, the functional levels as outlined above including TUG, STS, and PSFS will be re-evaluated. The approximate time spent is 30 minutes.

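### The by-arm adverse-effect table is not like for like: only the pregabalin arm is explicitly asked about side effects, and no enquiry is listed for either arm after the day-7 call

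*Combined protocol and SAP*

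**What the plan says.** The Analysis/Statistical Plan closes with one sentence on safety: "Adverse effects will be calculated for each treatment group and presented counts and percentages". How the events are to be found has to be read from the numbered study steps.

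- **Day of surgery (Dosing Schedule, step 6).** The team meets every participant, but the enquiry is restricted: "For those participants in the study medication arm, the research team member will also evaluate if they have" completed the medication schedule, and the team member is to "determine if they have noticed any side effects from the medication". For controls, the step lists only answering questions about staying in the study.
- **Call at about day 7 (step 8).** "All participants will be contacted by the study pharmacist about 7 days after surgery by telephone". Its aim is to learn "how the participant is faring with the study medication (if randomized to the study medication arm) and other pain medications". An exit rule for poor tolerability follows: "If the participant did not tolerate the study medication they will exit the study and continue to receive standard post-surgical care".
- **Week 6 (step 9).** At this visit "all participants will again complete the Knee Injury and Osteoarthritis Outcomes Score (KOOS), the PEG-3 pain survey, and the Central Sensitization Inventory (CSI) assessments". Opioid use and the functional tests are added, and step 10 then ends participation. No adverse-effect item is listed.
- **Dosing.** After the first post-operative week the schedule continues: "then (days 8-14) pregabalin 75mg twice daily".

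Controls proceed with usual peri-operative management (Protocol, step 4), and no placebo is described.

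**The concern.** Two adjacent percentages invite comparison, and they can be compared only if both groups were asked the same thing over the same period. Here they were not. Symptoms such as tiredness or dizziness can occur in the week before surgery without study drug. On the day of surgery such symptoms would be elicited from pregabalin participants and not from controls. Wording the question as effects of the medication also ties it to one arm, and participants know which arm they are in.

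Separately, the last listed enquiry comes while the pregabalin arm still has scheduled doses to take. Events in that last stretch, or after stopping, have no listed route into the table. At stake is whether the by-arm safety table can be read as a comparison at all. No efficacy analysis is involved.

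**Working it through.** The documents give no adverse-effect rate, so there is no figure of the plan's own to reproduce. The check has three steps.

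**1. Enquiry by contact and arm (from the numbered steps)**

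| Contact | Pregabalin arm | Control arm |
|---|---|---|
| Day of surgery (step 6) | Explicit side-effect question | None listed |
| Post-operative physical therapy (step 7) | Functional tests only | Functional tests only |
| Call, about day 7 (step 8) | Study drug and other pain medications | Other pain medications |
| Week 6 (step 9) | None listed | None listed |

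Explicit side-effect questions: pregabalin one, control none. Contacts with an adverse-effect item after the call: none in either arm.

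**2. Dosing after the last listed enquiry**

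The schedule has 7 days before surgery and 7 + 7 after it, 21 in all. For a call on post-operative day d, the share of dosing days still to come is (14 − d)/21.

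- d = 7: 7/21 = 33.3%
- d = 5: 9/21 = 42.9%
- d = 9: 5/21 = 23.8%

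The range from day 5 to day 9 is my assumption for a call at about 7 days.

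**3. What this can do to the table (illustration only)**

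Observed rate in an arm = p × w × c, where p is the true rate, w is the share of events falling before the last enquiry, and c is the capture of those events. Pregabalin capture is set to 1. All values of p, w and c are assumptions. The value w = 2/3 spreads events evenly over the 21 dosing days, which nothing in the documents supports in particular.

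| Case | Control c | Pregabalin | Control | Observed excess | True excess |
|---|---|---|---|---|---|
| A: p = 20% in both arms, w = 1 in both | 25 / 50 / 75% | 20.0% | 5.0 / 10.0 / 15.0% | 15 / 10 / 5 points | 0 |
| B: p = 40% v 20%, w = 2/3 in both | 25 / 50 / 75% | 26.7% | 3.3 / 6.7 / 10.0% | 23.3 / 20.0 / 16.7 points | 20 |
| C: p = 20% in both arms, w = 2/3 v 0.95 | 75% | 13.3% | 14.25% | −0.9 points | 0 |

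Case A isolates unequal asking: the false excess is p × w × (1 − c), positive whenever c is below 1. Case B adds a real drug effect and the late gap, and the observed excess is then too large, correct or too small depending on c. In case C coverage is poorer in the pregabalin arm, and the sign reverses. Unequal coverage is plausible because only that arm has doses after the call and only that arm can exit for not tolerating study drug, with no adverse-effect follow-up after exit described.

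**The case against.** Four arguments can be made against the point.

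- **Controls are not wholly unasked.** The call reaches them, and its stated aim includes how they fare with other pain medications. This stands: some control events will surface there, and a reader who infers that controls have no safety contact goes too far. It does not make the enquiry equal, because the call lists no general adverse-effect question and has no counterpart to the day-of-surgery question.
- **The late gap looks larger than it is.** Taking week 6 as day 42, no item is listed for 35 of 42 post-operative days (83%), and a reader might infer that most of the relevant risk period is unobserved. The documents do not support that: 28 of those 35 days fall after scheduled dosing ends on day 14. The more relevant figure is the 7 dosing days.
- **Absence in the text is not proof of absence.** The opening pages and consent pages were not available, and event definitions or reporting procedures could be there. This limits the statement that nothing is listed. It does not remove the restriction written into step 6.
- **The table is descriptive.** No test of adverse effects is planned, and the Analysis/Statistical Plan does not name them as a primary, secondary or exploratory outcome. This stands and sets the severity.

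**Conclusion.** The point holds as a minor one. Following the stated steps gives by-arm percentages that depend partly on who was asked, because the one explicit question is limited to the pregabalin arm by a written rule. In addition, 7 of 21 dosing days (33%; 24% to 43% for a call on day 9 to day 5) follow the last listed enquiry. The by-arm table would not be a like-for-like comparison.

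A reader might infer that the table will exaggerate the harms of pregabalin. That follows only if the true rates and the covered share of events are the same in both arms, as in case A. With a real drug effect or unequal coverage, the late gap can cancel or outweigh the inflation. The documents fix neither quantity, so the net direction and size cannot be determined, and the illustrative points are not estimates for this trial. The primary outcome, change in KOOS-ADL, is unaffected.

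**What to change.** Put the same short, neutrally worded adverse-effect question, not framed as effects of the medication, to all participants in both arms at the existing day-of-surgery, day-7 and week-6 contacts. At week 6 the question should cover the time since the call, with its recall limit stated: at day 42, post-operative days 8 to 14 lie 42 − 14 = 28 to 42 − 8 = 34 days back. In the Analysis/Statistical Plan, state that the table will show the number asked per arm at each contact. This also gives readers a usable denominator, which the section does not name.

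If controls are not asked, either label the table as not comparable between arms or report adverse effects for the pregabalin arm only. That fallback is a reporting edit.

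The cost is one question on existing forms, a sentence or two in the analysis plan and a few minutes per contact. No new visits are needed, and dosing and exit rules are untouched. Two limits remain and should be stated: week-6 recall is imperfect, and participants who have exited may not be reachable at later contacts.
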